9.4 DATA SOURCES

Medical Data Vision (MDV) clinical database. The database is health insurance claim database. As of end of July 2015, facilities: 200, patients: 10.95 million, which is covering approximately 12% of acute hospitals in Japan. Lab results are also available but number of hospitals providing with lab test results are limited.

Study period is from 01/01/2014 to 30/09/2016 in MDV database at the time of study protocol approval.

The MDV database is broadly representative of the Japanese population with similar distribution comparing with Japanese population; therefore we believe our study sample will provide reasonable description of the characteristics of patients treated with diagnosis of type 2 diabetes mellitus in the general Japanese population. There is research experience using the data, 19 publications, 5 conference presentations (as of August 2015).

9.5 STUDY SIZE

All available data from 01/01/2014 to 30/09/2016 will be included to ensure the maximum number of patient.

All patients with a prescription of OADs and DPP-4 inhibitors from 01/01/2014 to 31/08/2015 and a diagnosis of T2DM is estimated that approximately 9,890 and 7,579 patients respectively have been prescribed a study drug in the MDV database to be included in the study.

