Protocol date: 09 February 2017	Study number: 1218.178	Version/Revision: 1.0	Version/Revision date:
		
01/01/2014 to 31/08/2015 and a diagnosis of T2DM is estimated that approximately 9,890 and 7,579 patients respectively have been prescribed a study drug in the MDV database to be included in the study.
 
The power calculation has not been conducted as there will not be any hypothesis testing in the analysis. Data of MDV is from all DPC hospitals. Data is collected directly from hospitals, so it holds every data of all insurances.
 
Limitaion: Number of hospitals providing with lab test results are limited.
	
Data analysis:	
 • For the 1st objective, descriptive statistics of each compound and each class of OAD will be presented for the baseline demographic and clinical characteristics: 
 • Number of patients • Age (mean ± SE, mean ± SD) • Concomitant medications (drug prescribed at index day) : 
 • Use of biguanide (Yes/No) • Use of sulfonylurea (Yes/No) • Use of thiazolidinediones (Yes/No) • Use of glinide (Yes/No) • Use of α-GI (Yes/No) • Use of GLP-1RA (Yes/No) • Use of SGLT2 inhibitors (Yes/No) • Use of insulin (Yes/No) • Premedications (drug prescribed before index day): 
 • Use of biguanide (Yes/No) • Use of sulfonylurea (Yes/No) • Use of thiazolidinediones (Yes/No) • Use of glinide (Yes/No) • Use of α-GI (Yes/No) • Use of GLP-1RA (Yes/No) • Use of SGLT2 inhibitors (Yes/No) 		

Proprietary confidential information © 2017 Boehringer Ingelheim International GmbH or one or more of its affiliated companies

Name of company: Boehringer Ingelheim			
Name of finished medicinal product: If applicable, list centrally-authorized medicinal product(s) subject to the study.		Trazenta	
Name of active ingredient: List pharmacotherapeutic group(s){ACT codes} and active substance(s) subject to the study		A10N,A10H,A10J,A10K,A10L A10M	
Protocol date: 09 February 2017	Study number: 1218.178	Version/Revision: 1.0	Version/Revision date:

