9. RESEARCH METHODS

9.1 STUDY DESIGN

Study design:

- Descriptive cohort study

Comparison group

- OAD group, DPP-4 inhibitors group, SU group, BG group, TZD group, α -GI group, and Glinide group.

Strength of the study design

- Up-to-date information can be obtained and nationwide actual treatment status can be illustrated with using large-scale real-world database.

Analysis

- First analysis: type and dosage of drug prescribed for T2DM patients.
- [REDACTED]
- Main measures: number of patients, baseline characteristics at index month (age, sex), prior and concomitant use of glucose-lowering medications and insulin (type, dose), comorbidities (types and their percentages of patients), stage of RI defined by eGFR or serum creatinine value, glucose-lowering medications and their dosages (based on daily dose) for patients with RI, [REDACTED]
- [REDACTED]

Potential limitation

- The data held in MDV database is collected from DPC hospitals, not GP data. However they are including outpatient data because many of Japanese patients prefer to visit a hospital even though chronic disease.
- The rate of laboratory test data held in MDV database is limited. About 350,000 patients out of 2,600,000 patients (13.5%, April 2008 ~ April 2016) have laboratory data.
- The MDV database does not hold the time diagnosis of T2DM if it is out of study period. Therefore the onset date of diabetes or the first record of T2DM cannot obtain for all patients.
- The information on medication is based on prescribed record, not include adherence result. It means that exact dosage may not reveal actual dispensed prescription and dosage perfectly.
- Laboratory test date is not exactly matched with the index day of the first prescription of OAD. The sample size will have some impacts (reduction) to assure simultaneous timing of data. The latest lab result 30 days before the index date will be considered the status at the time of prescription
- All information of each patient is from consent given DPC hospitals. If patients have visits to other medical institutions, these data are not included in the MDV data.

- MDV database is composed of data from patients who hospitalized in DPC hospital so that more severe patient will be included in the database.

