9.2 SETTING

Medical Data Vision (MDV) clinical database is used.

Inclusion criteria

[figure not shown]
- Patients with T2DM (ICD code: E11 or E14).
- Patients must have their first prescription (defined as index date*) for any study drugs between 01/01/2014 and 30/09/2016.
- Patients must have at least 6 months enrolment verified by the presence of any record except for the study drug prescriptions within the database (look back period) prior to the index date for each drug.

Exclusion criteria

- Patients who were under 40 y.o. at the time of diagnosis of diabetes.
- Patients with record of type 1 diabetes mellitus (ICD code: E10).
- Patients who prescribed the study drugs during 6 month prior to index date for each drug.
- Patients whose mean visit interval are more than 92 days

*Index date is defined as follows:

- In case of comparing drugs within class, index date is defined as the date of first prescription for any study drugs as general name. Change of dosage is not counted as the index.
- In case of comparing drugs between class, index date is defined as the date of first prescription for study drug of class. Change of dosage is not counted as the index.

* The hospitalization period is not included in the mean visit interval.

Figure 1 Definition of Index data(date of first prescription for any study drugs)

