9.3.1 Exposures

Prescriptions for an OAD issued between 01/01/2014 and 30/09/2016 described below:

- DPP-4 inhibitors therapies:
 - Alogliptin
 - Alogliptin/Pioglitazone single-pill combination
 - Anagliptin
 - Linagliptin
 - Saxagliptin
 - Sitagliptin
 - Teneligliptin
 - Vildagliptin
- Sulfonylurea therapies:
 - Acetohexamide
 - Glyclopamide
 - Glibenclamide
 - Chlorpropamide
 - Tolbutamide Tablets
 - Tolbutamide Powders
 - Gliclazide
 - Glimepiride
 - Glimepiride Orally-disintegrating tablet
- Biguanide therapies:
 - Buformine
 - Metformin
- Thiazolidinedione therapies:
 - Pioglitazone
 - Pioglitazone Orally-disintegrating tablet
 - Glimepiride/Pioglitazone single-pill combination OD
 - Metformin/Pioglitazone single-pill combination OD
- α -GI:
 - Acarbose
 - Acarbose Orally-disintegrating tablet
 - Voglibose
 - Voglibose Orally-disintegrating tablet
 - Miglitol
 - Miglitol Orally-disintegrating tablet
- Glinide therapies:
 - Nateglinide

- Mitiglinide
- Repaglinide
- Mitiglinide/Voglibose single-pill combination

* Combined in general name if the drug has been sold in several brand name.

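### Renal stage rests on two incompatible creatinine windows: six months from the index date in section 9.3.3, 30 days before it in sections 9.1 and 9.9

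*Combined protocol and SAP*

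**What the plan says.** **Creatinine.** Section 9.3.3 (Covariates) defines stage of renal impairment by eGFR or serum creatinine, with cut-offs in Annex 3. It uses the most recent creatinine lying within six months of the index date and does not say whether that means before, after or both. Section 9.1, under potential limitations, says that the most recent laboratory result from the 30 days before the index date will stand for the patient's status at prescription. Section 9.9 repeats that sentence word for word. Section 11 describes the baseline characteristics as pre-treatment.

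**Where renal stage is used.** Section 9.1 lists stage of renal impairment, and drugs and daily doses in patients with renal impairment, among the main measures. Section 9.3.2.2 makes drug and daily dose, in view of renal cut-offs, the secondary outcome. Section 7 gives dose selection among patients with renal impairment as the aim.

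**Study size.** Section 9.5 states "All available data from 01/01/2014 to 30/09/2016 will be included to ensure the maximum number of patient", and section 9.4 agrees: "Study period is from 01/01/2014 to 30/09/2016 in MDV database at the time of study protocol approval". The estimate beside it is for a "prescription of OADs and DPP-4 inhibitors from 01/01/2014 to 31/08/2015 and a diagnosis of T2DM is estimated that approximately 9,890 and 7,579 patients", described as patients to be included in the study. The abstract gives the same figures.

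**The concern.** Both creatinine sentences are worded as rules for the same quantity, renal status when the drug was prescribed, and a programmer cannot follow both. Two analysts working from this protocol could report different sets of staged patients, and so different dose distributions by renal stage, each with support in the text. Laboratory data are already scarce: section 9.9 puts them at 13.5% of patients and section 7 at about 10%. Sections 9.1 and 9.9 also concede that aligning laboratory dates will shrink the sample, but the amount depends on which window is meant.

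The silence in 9.3.3 about direction adds a second ambiguity. Read literally, the latest value within six months either side could be one taken after treatment began, which would conflict with section 11.

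**Working it through.** **1. The rules side by side.** I read the 30-day sentence as a window of 30 days ending at the index date.

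| | 9.3.3 | 9.1 and 9.9 |
|---|---|---|
| Length | six months | 30 days |
| Side of index date | not stated | before |
| Value taken | latest | latest |
| Index day | not stated | not stated |

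**2. Ratio of lengths.** Six calendar months before an index date in the study period is 181 to 184 days. 181/30 = 6.03 and 184/30 = 6.13, so the windows differ about six-fold even if 9.3.3 looks only backwards.

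**3. What can differ.** If both windows look backwards, the 30-day window lies inside the six-month one. A patient with a result in the last 30 days gets the same latest value under either rule. The patients who differ are those whose last result is more than 30 days but no more than six months old: staged under 9.3.3, unstaged under 9.1 and 9.9. If 9.3.3 also admits later values, the value used can change as well.

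**4. Does the design settle it?** No. Section 9.2 requires a six-month look-back ("Patients must have at least 6 months enrolment verified by the presence of any record except for the study drug prescriptions within the database"), and either backward window fits inside it.

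**5. Illustration only.** Assume evenly spaced visits, creatinine drawn at each visit and no index-day result counted. Section 9.2 excludes only "Patients whose mean visit interval are more than 92 days", so mean intervals up to 92 days are admitted. With interval d, the number of earlier visits in a window of W days is floor(W/d):

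| d (days) | W = 30 | W = 181 to 184 |
|---|---|---|
| 30 | 1 | 6 |
| 31 | 0 | 5 |
| 60 | 0 | 3 |
| 92 | 0 | 1 to 2 |

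Under these assumptions a patient seen every 31 to 92 days is staged by one rule and not by the other. If index-day results count and exist, the same patient is staged under both.

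**6. Share affected.** It cannot be computed. The 13.5% (350,000/2,600,000 = 13.46%) and the 10% concern any laboratory data in the whole database, not creatinine inside a window in this cohort.

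**7. Side note on study size.** The 9,890 and 7,579 are database counts and cannot be rebuilt from the documents. Calendar arithmetic, inclusive:
- Estimate, 01/01/2014 to 31/08/2015: 12 + 8 = 20 months; 365 + 243 = 608 days.
- Study, 01/01/2014 to 30/09/2016: 12 + 12 + 9 = 33 months; 365 + 365 + 274 = 1,004 days.
- 608/1,004 = 60.6% of the days.

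**The case against.** **Section 9.3.3 should govern.** It is the covariate definition, while the 30-day sentence appears only in limitations lists, and 9.9 copies 9.1, so the repetition is not independent confirmation. This is fair, and a programmer might well choose 9.3.3. But the 30-day sentence is worded as an operating rule, no visible text ranks the two, and following 9.3.3 alone leaves direction and the index day open.

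**Later values are conjecture.** Largely accepted. Section 11 and the 30-day sentence both point to values before treatment, and nothing calls for later ones. The wording of 9.3.3 permits them, which is reason to close the gap but not evidence that they are intended.

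**Redaction.** Some objectives, analysis items and a subsection of 9.7 are blacked out and may contain a governing rule. This stands, and the point is limited to the visible text.

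**The illustration builds in its result.** It shows that the rules can diverge, not how often. A mean visit interval does not fix the gap just before the index date.

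**A stronger reading of the study size.** A reader might infer that the plan contradicts itself on its size, or undercounts patients by the 39.4% of days left out (396 of 1,004). The documents do not support this. The estimate carries its own dates, and days are not patients. The sentence also does not say whether the other 9.2 criteria were applied: the longer window would raise the count and unapplied criteria would lower it, so the direction of any error is unknown. The abstract says that no hypothesis is tested and no power calculation was made, all available patients enter, and 9.7.1 reports n for each compound and class.

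**Conclusion.** In the visible text, renal stage is defined by two windows that cannot both be followed. They differ about six-fold in length (181 to 184 days against 30) and can stage different patients. This is an error as written, not just missing detail, and it should be corrected before the renal outputs are programmed.

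Its reach is limited. It touches renal stage, dosing in patients with renal impairment and the secondary outcome. It does not touch the visible 9.7.1 table, which takes renal impairment from recorded diagnoses, so a reader who infers that the primary description is compromised goes too far. How many patients change status is unknown and cannot be derived. The conclusion assumes that the 30-day sentence describes a window ending at the index date and that no redacted passage sets precedence.

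The study-size estimate is a labelling matter only: a count over 20 of 33 months presented as the patients to be included. No result depends on it.

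**What to change.** 1. Reconcile sections 9.1, 9.3.3 and 9.9 into one creatinine window covering only values on or before the index date, in line with section 11. State its length and whether an index-day result counts. The choice of length is the sponsor's.
2. Report the number of patients staged under the chosen window, and repeat the renal-stage and dose outputs with the other length as a sensitivity analysis.
3. In section 9.5 and the abstract, label 9,890 and 7,579 as a feasibility count for 01/01/2014 to 31/08/2015, not the size of the planned study. Rerunning the forecast, forecasting all seven groups in 9.1 or tabulating baseline by creatinine availability is not needed.

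The cost is one agreed sentence in three sections, one extra run of the renal tables and a relabelled figure in two places. The downside is possibly fewer staged patients, if the shorter window is chosen or later values would otherwise have counted.

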9.6 DATA MANAGEMENT

Data were provided as electrical data formatted csv by Medical Data Vision Co., Ltd. SAS and Microsoft Excel were used for statistics.

9.7 DATA ANALYSIS

9.7.1 Main analysis

- For the primary objective, descriptive statistics of patients prescribed each compound and each class of OAD at least once will be presented for the baseline demographic and clinical characteristics:
 - Number of patients (n, % of total patients)
 - Age (mean ± SE, mean ± SD)
 - Sex
 - Concomitant medications (drug prescribed at index day) :
 - Use of biguanide (Yes/No)
 - Use of sulfonylurea (Yes/No)
 - Use of thiazolidinediones (Yes/No)

- Use of glinide (Yes/No)
- Use of α -GI (Yes/No)
- Use of GLP-1RA (Yes/No)
- Use of SGLT2 inhibitors (Yes/No)
- Use of insulin (Yes/No)
- Premedications (drug prescribed before index day):
 - Use of biguanide (Yes/No)
 - Use of sulfonylurea (Yes/No)
 - Use of thiazolidinediones (Yes/No)
 - Use of glinide (Yes/No)
 - Use of α -GI (Yes/No)
 - Use of GLP-1RA (Yes/No)
 - Use of SGLT2 inhibitors (Yes/No)
 - Use of insulin (Yes/No)
- Comorbidities:
 - Hypertension: Percentage of patients with a diagnosis of hypertension
 - Ischemic heart disease (IHD): Percentage of patients with a diagnosis of IHD
 - Myocardial Infarction (MI): Percentage of patients with a diagnosis of MI
 - Heart Failure (HF): Percentage of patients with a diagnosis of HF
 - Stroke: Percentage of patients with a diagnosis of stroke
 - Renal impairment: Percentage of patients with a diagnosis of renal impairment
 - Amputation: Percentage of patients with a diagnosis of amputation

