	
 • Use of insulin (Yes/No) • Comorbidities: 
 • Hypertension: Percentage of patients with a diagnosis of hypertension • Ischemic heart disease (IHD): Percentage of patients with a diagnosis of IHD • Myocardial Infarction (MI): Percentage of patients with a diagnosis of MI • Heart Failure (HF): Percentage of patients with a diagnosis of HF • Stroke: Percentage of patients with a diagnosis of stroke • Renal impairment: Percentage of patients with a diagnosis of renal impairment • Amputation: Percentage of patients with a diagnosis of amputation 		

Name of company: Boehringer Ingelheim			
Name of finished medicinal product: If applicable, list centrally-authorized medicinal product(s) subject to the study.		Trazenta	
Name of active ingredient: List pharmacotherapeutic group(s){ACT codes} and active substance(s) subject to the study		A10N,A10H,A10J,A10K,A10L A10M	
Protocol date: 09 February 2017	Study number: 1218.178	Version/Revision: 1.0	Version/Revision date:
Milestones:	Submission to IRB (Keio University)		10 th February 2017
	IRB (Keio University) meeting		17 th February 2017
	Registration to clinicaltrials.gov and ENCePP		28 th February 2017
	Start of data analysis		1 st March 2017
	Start of manuscript preparation		1 st March 2017
	End of data analysis		10 th March 2017
	Draft study report		31 st March 2017
	Final report of study results		20 th April 2017
	Submission of manuscript to Journal		26 th June 2017

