8. RESEARCH QUESTION AND OBJECTIVES

Research question:

To understand the prescription pattern in T2DM patients of each compound and each class for all OADs, available throughout study period i.e. DPP-4 inhibitors, sulfonylureas, biguanides, thiazolidinediones, α -GIs, glinides.

Study objectives:

1. To analyze the demographic and clinical characteristics of T2DM patients who have been treated with OADs

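### The medication rows listed in 9.7.1 cover five of the six study classes and leave out DPP-4 inhibitors, in both the concomitant and the premedication list

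*Combined protocol and SAP*

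**What the plan says.** Section 8 names six oral classes as the subject of the study: "DPP-4 inhibitors, sulfonylureas, biguanides, thiazolidinediones", followed by α-GIs and glinides. The comparison groups in 9.1 are those six plus an overall group: "OAD group, DPP-4 inhibitors group, SU group, BG group, TZD group", then α-GI and glinide. Section 9.3.1 lists DPP-4 inhibitors first among the exposures, with eight entries.

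Section 9.1 gives as one of the main measures "prior and concomitant use of glucose-lowering medications and insulin (type, dose"). Sections 9.3 and 9.3.3 repeat the variable, and 9.3.3 adds that drugs are identified by ATC code and drug name. None of the three leaves out a class.

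For the primary objective, 9.7.1 says that "descriptive statistics of patients prescribed each compound and each class of OAD at least once will be presented". It then itemises the rows. Two of the blocks are "Concomitant medications (drug prescribed at index day") and "Premedications (drug prescribed before index day"). Each has the same eight Yes/No rows: biguanide, sulfonylurea, thiazolidinedione, glinide, α-GI, GLP-1RA, SGLT2 inhibitor and insulin.

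The abstract carries the same scope ("descriptive statistics of each compound and each class of OAD will be presented for the baseline demographic and clinical characteristics") and the same two lists. The second ends at "Use of insulin (Yes/No"). No section gives a reason for leaving DPP-4 inhibitors out.

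**The concern.** The lists would suit a cohort made up only of DPP-4 inhibitor users, where a row for that class looks redundant. But 9.7.1 applies them to every compound and every class. A programmer who follows the text would describe the background treatment of patients starting a sulfonylurea, biguanide, thiazolidinedione, α-GI or glinide for every study class except one. The itemised list is therefore narrower than the variable the plan defines.

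These tables are the primary outcome in 9.3.2.1, and the research question is about prescription patterns. Section 7 reports a view among physicians that DPP-4 inhibitors are widely chosen, both alone and in combination. Co-use with the other five classes is part of the pattern the study sets out to describe.

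**Working it through.** The plan states no figure to reproduce, so the check sets the study classes against the listed rows and counts the tables that lack the row.

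**1. Rows against study classes (section 8 against 9.7.1; the abstract is identical)**

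| Study class | Concomitant row | Premedication row |
|---|---|---|
| DPP-4 inhibitors | no | no |
| Sulfonylureas | yes | yes |
| Biguanides | yes | yes |
| Thiazolidinediones | yes | yes |
| α-GIs | yes | yes |
| Glinides | yes | yes |

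Each list has 8 rows = 5 study classes + 3 others (GLP-1RA, SGLT2 inhibitors, insulin). Study classes without a row: 6 − 5 = 1.

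**2. Is it a loss in the published text?** No redaction mark falls inside either list in 9.7.1, and the abstract gives the same eight rows twice. Loss in redaction or extraction is an unlikely explanation.

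**3. Class tables that lack concomitant DPP-4 inhibitor use.** Five class tables (SU, BG, TZD, α-GI, glinide). An overall OAD table would be a sixth, but 9.7.1 commits only to compounds and classes; the overall table is inferred from the groups in 9.1.

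**4. Compound tables (entries in 9.3.1)**

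- As listed: 8 DPP-4 + 9 SU + 2 BG + 4 TZD + 6 α-GI + 4 glinide = 33. Non-DPP-4: 33 − 8 = 25.
- With dosage forms of the same drug merged: 8 + 7 + 2 + 3 + 3 + 4 = 27. Non-DPP-4: 27 − 8 = 19.

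So 25 of 33, or 19 of 27, compound tables would not report DPP-4 inhibitor co-use. The other 8 are DPP-4 compounds, whose tables would not show a second DPP-4 inhibitor on the index day.

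**5. Prior use under each reading of the washout.** Section 9.2 excludes patients prescribed the study drugs in the 6 months before the index date for each drug, and the wording allows three readings. The premedication heading sets no lower time limit, so earlier use on record counts under all three.

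- *Per drug:* any prior DPP-4 inhibitor use is possible in the other classes' tables and goes unreported. In a DPP-4 compound table, so does a recent switch from another DPP-4 inhibitor.
- *Per class:* the gap in the other classes' tables is the same. Within the DPP-4 class, only use more than 6 months before index can be missed.
- *Any study drug:* only use more than 6 months before index can be missed. Five of the eight listed premedication rows would then be empty for those 6 months, and 3 of 8 could still be filled.

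The index date is set for each drug (abstract) or by class (9.2), and the plan lists five rows that the third reading would leave empty for those 6 months. Both favour the first two readings without proving either. No reading affects co-use on the index day.

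**6. After the change.** Each list goes from 8 to 9 rows, the two together from 16 to 18, and coverage from 5 of 6 to 6 of 6 study classes.

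**The case against.** The strongest reply is that absence from 9.7.1 is not absence from the plan. Dose, serum creatinine and eGFR stage are also named as variables and do not appear in 9.7.1 either. The contents list shows a redacted entry directly after 9.7.1, and some objectives and parts of the analysis list in 9.1 are redacted too. Further medication tables may be there. This stands as a limit: the point covers the visible lists only. It does not explain why an itemised list with rows for five study classes and three non-study classes skips the sixth.

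Three stronger readings are tempting, and the documents do not support them.

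- A reader might infer that the omission defeats the study's stated rationale, because the abstract singles out DPP-4 inhibitors when it says data are insufficient. The shortage described there is of data on dose adjustment in relation to renal impairment, not on background DPP-4 inhibitor use among patients starting other classes.
- A reader might take the section 9.5 estimates as the size of the gap: 7,579 / 9,890 = 76.6%. The text does not say that the first count is a subset of the second. Even if it is, it counts patients prescribed a DPP-4 inhibitor, not patients whose co-use or prior use would go unreported.
- A reader might infer that the primary results would be wrong. The eight listed rows are unaffected, and the study tests no hypothesis.

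It can also be said that the premedication half depends on the washout. That is right for its extent. The washout does not explain the omission, since the other five study classes come under the same rule and keep their rows.

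**Conclusion.** The point holds as a gap in completeness. Both lists in 9.7.1, and their copies in the abstract, omit one of the six study classes although the plan's own definition of the variable excludes none. Following the text would leave DPP-4 inhibitor co-use out of the primary-outcome tables for five classes and 19 to 25 compounds, and out of an overall OAD table if one is produced. Co-use of a second DPP-4 inhibitor would be missing from the eight DPP-4 compound tables.

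The concomitant half rests on the text alone. The premedication row is missing in the same way, but how much it matters depends on the washout reading. The number of patients concerned cannot be derived from the documents. The conclusion assumes that the redacted sections do not already supply these rows. Severity is minor to should-fix: nothing planned is biased, but the gap is in the primary tables and costs almost nothing to close.

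**What to change.** Add a Yes/No row for DPP-4 inhibitor use to the concomitant list and to the premedication list, in 9.7.1 and in the abstract.

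For the concomitant list only, state that the index drug is not counted as its own concomitant medication, in every table including any overall OAD table. The heading refers to drugs prescribed on the index day, which permits counting the index drug, and the documents do not settle the matter. If it is counted, the own-class row is 100% Yes by construction in that class's table: five such rows now, six once DPP-4 inhibitors are added.

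Leave the premedication rows in plain wording. Restricting them to another drug of the same class would hide use of the same drug before the washout window, which the plain rows can show.

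The cost is two extra rows per table and one sentence of definition. The DPP-4 inhibitor drugs must already be identified for the exposure list in 9.3.1, so no new data are needed.
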